6.2.1. Causality assessment

The relationship between the use of the medical device (including the medical - surgical procedure) and the occurrence of each adverse event shall be assessed and categorized.

During causality assessment activity, clinical judgement shall be used and the relevant documents, such as the Investigator's Brochure, the Clinical Investigation Plan (CIP) or the Risk Analysis Report shall be consulted, as all the foreseeable serious adverse events and the potential

risks are listed and assessed there. The presence of confounding factors, such as concomitant medication/treatment, the natural history of the underlying disease, other concurrent illness or risk factors shall also be considered.

The above considerations apply also to the serious adverse events occurring in the comparison group.

For the purpose of harmonizing reports, each SAE will be classified according to four different levels of causality:

- 1. Not related
- 2. Possible
- 3. Probable
- 4. Causal relationship

The sponsor and the investigators will use the following definitions to assess the relationship of the serious adverse event to the investigational device, the comparator or the investigation procedure.

- 1. Not related: Relationship to the device, comparator or procedures can be excluded when:
 - the event has no temporal relationship with the use of the investigational device, or the procedures related to application of the investigational device;
 - the serious adverse event does not follow a known response pattern to the medical device (if the response pattern is previously known) and is biologically implausible;
 - the discontinuation of medical device application or the reduction of the level of activation/exposure - when clinically feasible - and reintroduction of its use (or increase of the level of activation/exposure), do not impact on the serious adverse event:
 - the event involves a body-site or an organ that cannot be affected by the device or procedure;
 - the serious adverse event can be attributed to another cause (e.g. an underlying or concurrent illness/ clinical condition, an effect of another device, drug, treatment or other risk factors);
 - the event does not depend on a false result given by the investigational device used for diagnosis9, when applicable; In order to establish the non-relatedness, not all the criteria listed above might be met at the same time, depending on the type of device/procedures and the serious adverse event.
- 2. Possible: The relationship with the use of the investigational device or comparator, or the relationship with procedures, is weak but cannot be ruled out completely. Alternative causes are also possible (e.g. an underlying or concurrent illness/ clinical condition or/and an effect of another device, drug or treatment). Cases where relatedness cannot be assessed, or no information has been obtained should also be classified as possible.

- 3. Probable: The relationship with the use of the investigational device or comparator, or the relationship with procedures, seems relevant and/or the event cannot be reasonably explained by another cause.
- 4. Causal relationship: The serious adverse event is associated with the investigational device, comparator or with procedures beyond reasonable doubt when:
 - the event is a known side effect of the product category the device belongs to or of similar devices and procedures;
 - the event has a temporal relationship with investigational device use/application or procedures;
 - the event involves a body-site or organ that
 - the investigational device or procedures are applied to;
 - o the investigational device or procedures have an effect on;
 - the serious adverse event follows a known response pattern to the medical device (if the response pattern is previously known);
 - the discontinuation of medical device application (or reduction of the level of activation/exposure) and reintroduction of its use (or increase of the level of activation/exposure), impact on the serious adverse event (when clinically feasible);
 - other possible causes (e.g. an underlying or concurrent illness/ clinical condition or/and an effect of another device, drug or treatment) have been adequately ruled out;
 - harm to the subject is due to error in use;
 - the event depends on a false result given by the investigational device used for diagnosis, when applicable;

In order to establish the relatedness, not all the criteria listed above might be met at the same time, depending on the type of device/procedures and the serious adverse event.

The sponsor and the investigators will distinguish between the serious adverse events related to the investigational device and those related to the procedures (any procedure specific to the clinical investigation). An adverse event can be related both to procedures and the investigational device. Complications caused by concomitant treatments not imposed by the clinical investigation plan are considered not related. Similarly, several routine diagnostic or patient management procedures are applied to patients regardless of the clinical investigation plan. If routine procedures are not imposed by the clinical investigation plan, complications caused by them are also considered not related.

In some particular cases the event may not be adequately assessed because information is insufficient or contradictory and/or the data cannot be verified or supplemented. The sponsor and the Investigators will make the maximum effort to define and categorize the event and avoid these situations. Where an investigator assessment is not available and/or the sponsor remains uncertain about classifying the serious adverse event, the sponsor should not exclude the relatedness; the event should be classified as "possible" and the reporting not be delayed.

Particular attention shall be given to the causality evaluation of unanticipated serious adverse events. The occurrence of unanticipated events related could suggest that the clinical investigation places subjects at increased risk of harm than was to be expected beforehand.

6.2.2. Reporting timelines to Competent Authorities by sponsor

For all reportable events which indicate an imminent risk of death, serious injury, or serious illness and that requires prompt remedial action for other patients/subjects, users or other persons or a new finding to it: immediately but not later than 2 calendar days after awareness by sponsor of a new reportable event or of new information in relation with an already reported event.

Any other reportable event or a new finding/update to it: immediately, but not later than 7 calendar days following the date of awareness by the sponsor of the new reportable event or of new information in relation with an already reported event.

6.2.3. Report to whom

Reportable events must be reported all at the same time to all national competent authorities where the clinical investigation is authorized to start or has commenced.

6.3 Procedures for reporting specific events

6.3.1 Adverse event (AE) and adverse device effect (ADE)

Subjects will be carefully monitored during the clinical investigation for possible AEs and ADEs. The period of observation for AEs and ADEs extends from signing of the Informed Consent Form (ICF) until the subject's last visit. Any medical occurrence between the time the ICF is signed and the first treatment with the investigational medical device is classified as an AE or ADE and must be documented in the subject's file and in the eCRF. New AEs or ADEs reported to the investigator during the observational period (i.e., after the start of treatment with the investigational medical device) must also be documented, treated, and followed.

Any AE, ADE, and/or device deficiency observed during study conduct will be fully investigated, documented, and followed until the event is either resolved, until the condition stabilizes, until the event is otherwise explained, or the subject is lost to follow-up.

The investigator will assess and record any AE or ADE in detail in the subject's file (medical record) and in the eCRF AE report form. The information will be passed on to the sponsor/CRO where the assessment of AE would be done.

All details should be reported by the investigator to Sinclair Vigilance team ([contact]) and AESCULAPE CRO Clinical Safety Management ([contact]).

6.3.1.1. Determining severity/intensity

The investigator is required to grade the severity/intensity of each AE. The clinical severity/intensity of an AE will be classified as follows:

- Mild: Signs and symptoms that can be tolerated easily. Symptoms can be ignored and disappear when the subject is distracted.
- Moderate: Signs and symptoms that cause discomfort and interfere with normal functioning but are tolerable. They cannot be ignored and do not disappear when the subject is distracted.
- Severe: Signs and symptoms that affect usual daily activities and incapacitate the subject, thereby interrupting his/her daily activities.

The definitions above are difficult to apply for some data (e.g. clinically relevant laboratory values that are documented and evaluated on the eCRF AE report form). In such situations, the investigator should exercise medical and scientific judgment.

6.3.1.2. Determining outcome

The reportable outcomes and/or sequelae of an AE may include the following:

- Recovered/resolved
- Recovering/resolving
- Not recovered/not resolved
- Recovered/resolved with sequelae
- Fatal
- Unknown

NOTE: If a subject experiences more than one AE, only the AE leading to death will be attributed with a "fatal" outcome.

6.3.2 Serious adverse event (SAE) and serious adverse device effect (SADE)

The investigator must report all SAEs/SADEs, irrespective of severity, that occur during the observational period within 72 hours to [contact] and [contact] whether they are considered related or not related to the investigational device.

The following information should be provided:

- Status (new reportable event, update, unchanged)
- Investigator/investigational site name/country
- Subject ID/age/gender

- Event description
- Event classification (seriousness)
- Date of onset
- Investigational device name/date of implantation
- Investigational device location
- Causality or relationship of investigational device
- Action/treatment/outcome

When the sponsor first receives notice of the SAE/SADE, the sponsor will conduct an assessment of the SAE/SADE and, if applicable, report the results of such evaluation to regulatory agencies, IECs/IRBs, and investigators.

Follow-up SAE/SADE reports should be sent without delay to the sponsor or designee as an SAE form (marked as a "follow-up" report). The SAE/SADE must be followed until the SAE/SADE is resolved/recovered or a plausible explanation is available.

In the case of a reportable death, the investigator shall make every effort to obtain a copy of the autopsy report and/or death certificate. The investigator will be required to review any postmortem findings, including histopathology, and provide a synopsis of all pertinent findings by updating the SAE form.

SAEs/SADEs occurring after the end of the observational period will need to be reported if the investigator considers the event to be related to the investigational medical device. These reports generally will not be entered into the investigation database. Following the database lock for the study, all ongoing SAEs/SADEs will be followed until resolution or stabilization under the responsibility of the investigator per his/her standard of care.

Note that in case of pregnancy, an SAE will be completed and sent within 72 hours to Sinclair Vigilance team ([contact]) and Aesculape CRO Clinical Safety Management ([contact]).

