Procedures: Approach, Screening, Consent and Enrolment	Potentially eligible individuals will be approached by authorized physicians and/or local research teams during a (routine) appointment or advertisement. Written consent will be obtained in compliance with ICH-GCP, ISO 14155:2020, the local regulatory and the legal requirements from all potential subjects, once they have been given sufficient time to consider their participation in the study. Consent will include permission to retain contact details at the clinical site, which will enable the Sponsor, via the investigator, to inform the study subjects about a potential product recall or possible participation in future intervention/research studies. After informed consent has been obtained, the subjects will be screened based on the inclusion/exclusion criteria. If the criteria are met, the subject will be assigned in the appropriate treatment arm (i.e. MaiLi Volume or MaiLi Extreme) and enrolled in the study.

Procedures: Treatment Period Procedures: Follow-up Period	The subject will receive the corresponding treatment (i.e. MaiLi Volume or MaiLi Extreme) by a slow injection into the subcutaneous fat tissue or into the supraperiostic zone in the appropriate area of the face. The administration of the treatment will be done only by an authorized physician in accordance with local legislation. All instructions are clarified in the 'Instruction for Use' card. In addition, a video training will be used to explain the different procedures of the injection technique for each treatment area. These treatment instructions are important to standardize the application of the dermal filler as much as possible. There are 6 follow-up visits to assess safety and efficacy at week 2 (only safety), month 3, month 6, month 12, month 18, and month 24. At these follow-up visits, the effect of the
Criteria for Withdrawal of Participants	All subjects are free to withdraw their participation in this study at any time, for any reason and without penalty or loss of benefits to which the subject was otherwise entitled. The Case Report Form (CRF) has to be completed up to the time of withdrawal. The following withdrawal-related data has to be recorded in the CRF: 1. The date of last follow-up visit or withdrawal 2. Reason for withdrawal 3. Possible relation to the study treatment

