The compliance of the risk analysis and the Instruction for Use (IFU) of MaiLi Volume/Extreme devices (MaiLi Europe IFU-0002¹⁹) to the State-of-the-Art has been checked. The risks identified by Kylane Laboratories have all been mitigated to an acceptable risk level. For these risks, the benefit/risk ration is considered as acceptable for the use of MaiLi Volume/Extreme to the intended purpose "to modify the anatomy of the face area and/or to alleviate for a physiological process" and to specific intended uses of each device of the range, as long as users are appropriately warned of known limitations and risks associated with these devices.

Furthermore, the benefits of MaiLi Volume/Extreme outweigh the risks, as determined by the robustness of the effectiveness results, the lack of long-term sequelae, and the high subject satisfaction. No new risks have been identified by screening the international and national public databases, and do not need to be taken into consideration in the risk analyses of MaiLi Volume/Extreme products. The risks of short term adverse events outcomes seen after injection and rare adverse events are sufficiently well understood for subjects to make informed decisions about devices use. Moreover, the Instruction for Uses (IFUs) correctly describe the indications of the MaiLi Volume/Extreme devices as supported by sufficient clinical data.

If the subject has ever suffered from herpes infection, the risk of herpes reactivation following dermal filler injection has been reported to about $1.5\%^{20}$.

Side effects of MaiLi Volume/Extreme (MaiLi Europe IFU-0002 19)

Events which are naturally resolve within one week in most cases include:

- Injection-related events and/or inflammatory reactions such as (bleeding, skin redness (erythema), bruising (haematoma), swelling (oedema), and infection which may be associated with local pain or itching (pruritis) occurring after injection)
- Hardness (induration)/lump /granuloma at injection site
- Sensitivity at the injection site
- Skin coloration or discoloration (ecchymosis) at the injection site

Undesirable immediate/ delayed onset effects (non-exhaustive list):

- Immediate or delayed hypersensitivity to hyaluronic acid and/or to lidocaine.
- Nodule, abscesses or granuloma.

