5.1.5. End of Study (EoS)/ Premature Discontinuation Visit

- The subjects will come to the Investigator's office.
- They will bring back their completed subject diary.
- Collection of the eventual adverse events and concomitant treatments.

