8. SAMPLE SIZE AND STATISTICAL METHODS

8.1. Determination of Sample Size

The study population will include all subjects who are enrolled, and the entire study population will be included in statistical analysis.

Average Efficacy=85% Lower bound of 95% Confidence Interval (CI) =65% Clinical Margin=-20% Alpha=5% Power= 80% (Beta =0.20)

Considering 20% dropout rate, a total of 168 subjects (42 per site; a minimum of 36 per site respectively), to meet a completed study size requirement of 140, will be recruited.

- Mild to significant facial volume deficit (mid-face area) (n=60 (50), MaiLi Volume 30 (25) subjects and MaiLi Extreme 30 (25) subjects)
- Mild to moderate jawline ptosis (n=36 (30), MaiLi Extreme)
- Minimal to severe chin retrusion (n=36 (30), MaiLi Extreme)
- Minimal to severe temporal hollowing (n=36 (30), MaiLi Volume)

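### For subjects who leave early, the default in section 6.3.2 keeps device-related SAE reports received before month 24 out of the study database

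*Protocol*

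**What the plan says.** Section 6.3.1 sets the window subject by subject: "The period of observation for AEs and ADEs extends from signing of the Informed Consent Form (ICF) until the subject's last visit". No other end point for adverse event observation is given.

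Section 6.3.2 governs what follows: "SAEs/SADEs occurring after the end of the observational period will need to be reported if the investigator considers the event to be related" to the device. It then adds: "These reports generally will not be entered into the investigation database". The word 'generally' leaves room for exceptions, but no criterion for them is stated.

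For a subject who withdraws, the synopsis (Criteria for Withdrawal of Participants) says: "The Case Report Form (CRF) has to be completed up to the time of withdrawal". Section 5.1.5 provides for adverse events to be collected at a premature discontinuation visit ("Collection of the eventual adverse events and concomitant treatments"). It describes no contact after that visit.

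The primary objective (section 2.1, repeated in section 8.2) includes safety, through all adverse events, SAEs and unanticipated device effects in post-treatment follow-up. The study runs for 24 months. Section 3 lists undesirable effects of immediate or delayed onset, among them: "Nodule, abscesses or granuloma".

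**The concern.** The cut-off for database entry depends on when a subject leaves, not on time since injection. Take a subject who leaves at month 3 and has a related serious event at month 10. The investigator judges it related and reports it, and the sponsor receives it while the study is still running. By default it is not entered. The same event in a subject still attending would be entered.

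The reports concerned are serious, judged related to the device, and later in onset than that subject's last visit. A 24-month post-market study of a filler with recognised delayed effects has good reason to show such events. The pilot study reported no SAE over 12 months (section 3), so even a single event would be informative in the final report.

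**Working it through.** **1. How many subjects could be affected.** Section 8.1 gives 140 completers, 20% drop-out and 168 recruited. The recruitment figure reproduces as 140 × 1.20 = 168. Two readings of the number of early leavers follow:

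- 168 − 140 = 28 (28/168 = 16.7%)
- 0.20 × 168 = 33.6, about 34 (20%)

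**2. How the rules combine.**

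| Step | Completer | Leaves early |
|---|---|---|
| Observation ends (6.3.1) | month 24 | last visit attended |
| CRF completed to (synopsis) | month 24 | withdrawal |
| Later related SAE/SADE reported (6.3.2) | yes | yes |
| Entered in database (6.3.2) | generally not | generally not |
| Can the non-entered onset lie within 24 months of injection? | no | yes |

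Section 6.3.1 also requires events to be followed until resolution or stabilisation. That applies to events observed during study conduct. It does not bring in a new event that begins after the subject has left.

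**3. Size of the window.** Planned subject-months = 168 × 24 = 4,032. Share after exit = leavers × (24 − m) / 4,032, where m is the mean exit month. The protocol does not give m, so a range is assumed:

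| m (assumed) | 28 leavers | 33.6 leavers |
|---|---|---|
| 3 | 588 / 4,032 = 14.6% | 705.6 / 4,032 = 17.5% |
| 6 | 504 / 4,032 = 12.5% | 604.8 / 4,032 = 15.0% |
| 12 | 336 / 4,032 = 8.3% | 403.2 / 4,032 = 10.0% |
| 18 | 168 / 4,032 = 4.2% | 201.6 / 4,032 = 5.0% |

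This is follow-up time lost through drop-out. It marks where the rule could act, not how many known events are excluded.

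**4. Order of magnitude of events (illustration only).** The protocol gives no SAE rate. Assume a 24-month risk r of a delayed related SAE, with a fraction f of that risk falling after exit. The expected number among leavers is leavers × r × f:

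- low: 28 × 0.005 × 0.25 = 0.035
- middle: 28 × 0.01 × 0.5 = 0.14
- high: 34 × 0.02 × 0.75 = 0.51

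These figures suppose that every such event is reported to the site. People no longer attending will report fewer, so the number of known events kept out would be lower still.

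**The case against.** Several points on the other side have force.

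- **The events are not lost.** Omission is a default, the reports still go to the sponsor, and section 6.3.2 has the sponsor assess them and report onward where applicable. This stands: safety surveillance is intact. What the default affects is the study dataset.
- **There is no contradiction with the objective.** A subject who has left can be said to be no longer in follow-up, so the per-subject cut-off is compatible with section 2.1. Section 6.3.1 also glosses the observational period as time after treatment starts, with no end date. This too stands, so the point concerns a poorly chosen default, not an inconsistency. The only stated end is still the last visit.
- **A downward-biased SADE rate.** A reader might infer this from section 8.1, which says that "the entire study population will be included in statistical analysis", on the view that leavers stay in the denominator while their events are dropped. The sentence sits under sample size and defines no safety denominator. Exposure-adjusted incidence may be specified in an analysis plan not shown here. The inference is not supported. However, no choice of denominator can count an event that was never entered.
- **A 10–15% loss of safety data caused by the rule.** This might be read from the table above, but that time is missing because subjects left.
- **The clinical examples.** Nodule, abscess and granuloma are listed as undesirable effects, not as serious ones, and fall under section 6.3.2 only if they meet the SAE definition. A late vascular event would be a poor example, because the guideline in Appendix 8 describes occlusion as often immediate, or appearing hours or days later.
- **Extending observation to 24 months for everyone.** This would import duties to monitor all adverse events, and to report unrelated SAEs, in people the site no longer sees. The objection is sound, and the fix below avoids it.

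**Conclusion.** The point holds in a limited form. For the planned 28 to about 34 early leavers, the default keeps known, device-related SAEs/SADEs with onset within 24 months of injection out of the dataset used for the primary safety objective, and no other section repairs this. For completers the rule needs no change.

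The expected number of such events is small and cannot be quantified from the protocol. The window in which the rule could act is about 8–10% of planned subject-months if mean exit is month 12, and 12.5–15% if it is month 6. Both exit times are assumptions. The documents do not support reading the rule as absolute, as hiding events from the sponsor, or as producing a bias of that size. The change is worth making because it is nearly free and concerns serious events already known to be related.

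**What to change.** Leave the observation period in section 6.3.1 as it is. In section 6.3.2, limit the no-entry rule to reports with onset more than 24 months after injection, or received after database lock.

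Add that any SAE/SADE the investigator considers related to the device, with onset within 24 months of injection and received before lock, is entered with an after-withdrawal flag, where consent and data law permit. Report these events with the primary safety results, but display them separately from events collected at visits.

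The cost is a sentence or two in section 6.3.2 and one eCRF flag. No extra visits or active follow-up are needed, because the reports already reach the sponsor. There are two downsides. The flagged events are passively ascertained, which is why they need a separate display, and the reported SADE count may be slightly less favourable. The change does not recover follow-up lost to drop-out.
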